## ***Data Analysis***

Randomized groups will be assessed for balance on baseline characteristics using the standardized differences, defined as the difference in means or proportions divided by the pooled standard deviation. An absolute standardized differences  $> 0.10$  will be considered as imbalanced. We will use modified intent-to-treat such that all randomized patients receiving any of the study intervention (either one, even if the incorrect treatment was applied) will be included in the primary analyses.

**Primary outcome.** We will assess the treatment effect of NOL guided analgesic management versus routine care on mean pain score with the first 60 minutes of the recovery period using a linear mixed effects model adjusting for within-patient correlation across the 7 time points, and fixed effects for intervention, time (as categorical) and the stratification variable of pre-operative chronic opioid use. We will also assess the treatment-by-time interaction. We will decide on the most appropriate correlation structure empirically, using the AIC criterion, and considering either AR(1), exchangeable, or other correlation.

**Sensitivity analysis.** As a sensitivity analysis we will assess the treatment effect on pain score using a mixed effects proportional odds model in which we consider patient as a random effect while estimating the proportional odds ratio for patients having a better outcome on NOL than standard care, again adjusting for the stratification variable.

**Secondary outcome.** We will assess the treatment effect of NOL versus routine care on the proportion of patients with pain score less than 5 (i.e., 0-4) across the 7 time points using a generalized linear mixed effects model with a binary outcome ( $<5$  or  $\geq 5$ ), log link

(to be able to estimate relative risk), patient as random effect and modeling the within-subject serial correlation using an R matrix (considering autoregressive AR(1), exchangeable and unstructured correlation structures), with treatment group and the stratification variable as fixed effects. We will also assess the treatment-by-time interaction. Results will be reported as the relative risk (95% CI) of having a “good” pain score over time in NOL versus routine care.

**Exploratory outcome 1.** We will assess the treatment effect on the first exploratory outcome of number of analgesic rescue boluses using either a negative binomial regression (for count data), or else a proportional odds logistic regression if the negative binomial distribution is not a good fit to the data. In either case we will again adjust for the stratification variable.

**Exploratory Outcome 2.** We will assess the treatment effect on the Ramsey score measured at 10 minute intervals for during the first 60 minutes using a mixed effects proportional odds model to adjust for the within-patient correlation in the same manner as described for the sensitivity analysis for the primary outcome. We will test whether NOL is noninferior to routine care on the Ramsey score using a noninferiority delta of 1.2 for the proportional odds ratio, such that NOL will be deemed noninferior if the upper confidence limit for the odds ratio is less than 1.2. This will be accompanied by a 1-sided statistical test for noninferiority using the method described in Mascha and Sessler (2011), in which we use the parameter estimate and standard error of the treatment effect from the mixed effects model as well as the noninferiority delta in the test statistic, as

$$T_{NI} = \frac{\hat{\beta}_1 - \delta}{SE_{\hat{\beta}_1}}, \text{ where } \hat{\beta}_1 \text{ is the estimated log-odds ratio, } SE_{\hat{\beta}_1} \text{ is the estimated standard error, and } \delta \text{ is}$$

the log (delta), or log (1.2).

**Exploratory Outcome 3.** We will assess the treatment effect (in form of a hazard ratio) on the time to emergence from anesthesia using a Cox proportional hazards regression model adjusting for the stratification variable. We will check the proportional hazards assumption graphically and with the treatment-by-log (time) interaction. In presence of an interaction the treatment effect will be assessed using the log-rank test from a Kaplan-Meier analysis.

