## Background

Opioid requirements in hospitalized patients varies at least ten-fold depending on a host of factors, many of which are unknown to clinicians or poorly characterized in medical records. Important factors include genetic sensitivity, alcohol consumption, previous opioid use, pain intensity etc. Even within specific categories, say chronic opioid users, there is tremendous variation in sensitivity — and thus opioid requirement under various conditions.

In most situations, patients can simply be queried about pain, and their responses used to guide analgesic administration. But during anesthesia, patients do not experience pain (a conscious response). But patients nonetheless clearly experience and respond to nociception even during general anesthesia. Increases in blood pressure and heart rate roughly indicate when patients are experiencing nociceptive stress, but neither is reliable. No other routine anesthetic monitors provide useful indications of nociceptive intensity.

Even experienced anesthesiologists cannot reliably predict or estimate opioid requirements in individual patients. Consequently, most routinely give small amounts of opioid during general anesthesia, and often give a bolus of a slow-onset, long-acting opioid such as morphine or hydromorphone at the end of surgery to provide analgesia during the initial hours of post-anesthetic recovery. The doses given, while reasonable *on average*, often prove inadequate or excessive for individual patients. Those given too much awaken slowly at the end of anesthesia and may breathe poorly; those given inadequate doses suffer intense pain upon awaking and it often takes many boluses of opioid and considerable time to control their pain.

There are now several devices that estimate nociception during general anesthesia including the Surgical Pleth Index, pupillary reflexes, galvanic skin responses, and heart-rate variability. The best-validated system is the PMD-200 system from Medasense (Ramat Gan, Israel). It is comprised of a console and designated finger probe and a single-use sensor. The PMD-200 acquires 4 signals: photoplethysmography, galvanic skin response, accelerometry, and skin temperature. Based on a random forest analysis, the device generates the NOL index. The intended use of NOL is to assess nociception input during general anesthesia.

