## **Measurements**

Demographic and morphometric characteristics will be recorded, including sex, age, race, height, weight and opioid use in the last month (estimated morphine equivalents). Anesthesia clinicians cannot be blinded since they will need to titrate opioid administration to NOL. However, all postoperative care and evaluations will be fully blinded to randomization, thus preventing measurement bias. There will thus be separate teams of investigators for the intraoperative and postoperative portions of the trial.

All routine anesthetic monitoring will be used, and the results recorded electronically. Blood pressure will be evaluated continuously with an arterial catheter if clinically indicated; otherwise, blood pressure will be evaluated oscillometrically at 3-

minute intervals. Anesthetic drugs including end-tidal sevoflurane concentration, type and duration of surgery will also be recorded electronically at one-minute intervals. Inadequate analgesia will be defined by systolic pressure  $\geq 140$  mmHg, heart rate exceeding 90 beats/min, MAP  $< 65$  mmHg. Vasoactive drugs and episodes and duration of hypotension (mean arterial pressure  $< 65$  mmHg, occurrences of MAP  $< 60$  & MAP  $< 55$ ) will be recorded. Muscle-relaxant administration will be recorded as well.

During surgical stimulation under general anesthesia, a NOL of zero indicates no nociceptive response, and NOL of 100 indicates extreme nociceptive response. NOL values below 25 represent nociception/anti-nociception balance, suggesting either no nociception in the absence of noxious stimuli, or effective analgesia in the presence of noxious stimuli. NOL values are recorded by the Medasense monitor at 5-second intervals.

The clock on the NOL monitor will be synchronized to that driving the electronic record. Nociception will be continuously evaluated in all participating patients. However, values will be blinded to clinicians when patients are assigned to the routine opioid management group.

We will record the time of reversal agent administration wrist, the time at which sevoflurane is discontinued, along with the end of surgery (last stitch), eye opening, and extubation. Discontinuation of sevoflurane will be considered the end of anesthesia and the beginning of recovery.

The following will be recorded on the PMD-200 monitor, using the EVENTS button, as accurately as possible:

1. Medications administration:
  - a. Fentanyl
  - b. Vasoactive drugs

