### **Sample size justification.**

**Pilot patients:** N=21 pilot patients were enrolled prior to the start of the study to familiarize the study team with the protocol and identify any systematic issues that might result in protocol modifications. In the below sample size calculations we used data on these patients to help estimate the standard deviation of the primary outcome (pain score) and the within-subject correlation on the pain score across the 7 measurement times.

**Required Sample Size.** We plan the study to have 90% power at the 0.05 significance level to detect a difference in mean pain score of 1.25 or more between groups when measured over 10 minutes intervals during the first 60 minutes in the recovery period and analyzed using a linear mixed effects regression model. Based on our pilot study data (N=21) and previous work (SOLAR study report, Figure 1) we estimate the standard deviation of the pain score to be about 2.5 and the within-subject correlation to be approximately 0.60 when assumed to be exchangeable across measurements. Making these assumptions we would need a total of 116 patients before accounting for interim analyses, and a maximum of 144 after adjusting for planned interim analyses at each 1/4 of the maximum sample size. We therefore plan to randomize and enroll a maximum of 144 patients under these assumptions.

**Interim analyses.** We will conduct interim analyses for efficacy and futility at each 1/4 of the maximum sample size using a group sequential design and conservative gamma spending function parameters of -2 for efficacy and 0 (more aggressive) for futility. If the alternative hypothesis effect size (1.25 point difference) is true in the population sampled from, with the planned sample size we will cross an efficacy or futility boundary at each of the 4 looks with respective cumulative probabilities of 0.16, 0.50, 0.78 and 1.0.

Z-statistic boundaries for efficacy (futility) will be  $> 2.80$  ( $\leq 0.156$ ),  $> 2.58$  ( $\leq 0.667$ ),  $> 2.34$  ( $\leq 1.42$ ), and  $> 2.09$  ( $\leq 2.09$ ). The average total sample size across many simulations, assuming the alternative hypothesis is true (a true difference of 1), is N=64.

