**Simulations with Effect Size Larger Than Planned.** With the given design and corresponding stopping rules, if the true effect size (difference of 1.25 in mean pain score) is large than planned, the probability of crossing an efficacy boundary earlier in the trial will be proportionately increased. For example, if the true difference is 1.5, the cumulative probability of crossing a boundary (either efficacy or futility) in the 1st through 4th looks will be approximately 0.21, 0.62, 0.91 and 1.0, with average total sample size across many simulations was 81 patients.

**Internal Pilot Study to Reassess Standard Deviation and Within-Patient Correlation.** At the second interim analysis we will conduct an internal pilot study to reassess the standard deviation and within-patient correlation using the observed data for the primary outcome. Without considering the observed treatment effect, in a blinded fashion, we will use the observed within-patient correlation from the linear mixed effects model and the standard deviation at each time point to reassess the maximum required N to have 90% power at the 0.05 significance level to detect a difference of 1.25 or more in pain score. If the required sample size is at least 10% higher than initially planned, the Executive Committee will decide whether to recommend that the maximum sample size be

increased to maintain 90% power. There is no statistical penalty for this internal pilot re-estimation of the within-patient correlation “nuisance parameter”.

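### Should the primary pain model also adjust for last-month morphine equivalents, and not only for the chronic-opioid stratum?

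*Combined protocol and SAP*

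**What the plan says.** Under Data Analysis, the primary outcome is analysed by a linear mixed model over seven time points with "fixed effects for intervention, time (as categorical) and the stratification variable of pre-operative chronic opioid use". The proportional-odds sensitivity analysis, the secondary model, and the models for exploratory outcomes 1 and 3 also adjust for that stratum and for no other baseline variable. Measurements lists "opioid use in the last month (estimated morphine equivalents" among the baseline characteristics to be recorded, but no model uses it. Baseline balance is described with standardized differences, and no adjustment depends on the result.

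Background says of opioid requirement: "Important factors include genetic sensitivity, alcohol consumption, previous opioid use, pain intensity etc". It adds: "Even within specific categories, say chronic opioid users, there is tremendous variation in sensitivity".

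The sample size section states: "We plan the study to have 90% power at the 0.05 significance level", for a difference of 1.25 points. It plans "interim analyses for efficacy and futility at each 1/4 of the maximum sample size", that is at 36, 72, 108 and 144 patients.

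**The concern.** In a linear model, a prognostic baseline covariate reduces the residual variance and so narrows the interval for the treatment effect at no cost in patients. The plan names previous opioid use as important and stresses how much chronic users differ from one another. It records a graded measure of that use, yet the primary model sees only a yes/no stratum. A reader may conclude that the model discards information the sponsor itself considers relevant.

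Power, expected sample size and precision would be at stake. If the term explained a further 10% of the variance of patient means, power would be 0.925 instead of 0.904, and the 95% interval half-width at 144 patients would be 0.63 instead of 0.66.

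**Working it through.** **Inputs.** From the sample size section: SD 2.5, exchangeable correlation 0.60, difference 1.25, efficacy boundaries 2.80/2.58/2.34/2.09, futility boundaries 0.156/0.667/1.42/2.09. From Data Analysis: seven time points. Not in the document, hence assumed: the share of variance (R²) that morphine equivalents explain beyond the stratum, and the proportion of chronic users.

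**1. The plan's own figure.** The variance of a patient's mean over m scores is SD²·(1+(m−1)ρ)/m.
- m = 7: 6.25 × 4.6/7 = 4.107, SD 2.027. A two-sided 0.05 test at 90% power needs 112 patients (normal) or 114 (t-based).
- m = 6: 6.25 × 4.0/6 = 4.167, SD 2.041. This needs 114 or 116.

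The printed 116 is thus reproduced without any covariate gain. Gamma spending with non-binding futility inflates it by 1.219: 116 × 1.219 = 141.4, close to the printed 144.

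**2. Power of the planned model.** With V = 4.107, the variance of the treatment estimate at n patients is 4V/n. At n = 36 it is 0.456, so SE = 0.676 and the expected Z is 1.25/0.676 = 1.85. First-look efficacy stopping is P(Z > 2.80) = 0.171, and futility stopping is P(Z ≤ 0.156) = 0.045. Carried through all four looks by numerical recursion, power is 0.904 and expected N is 83.5. The half-width at 144 is 1.96 × √(4 × 4.107/144) = 0.66.

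This recursion does not match the printed crossing probabilities. It gives 0.171 + 0.045 = 0.216 at the first look, where the plan prints 0.16. The printed 0.16/0.50/0.78 imply an expected N of 36 × (1 + 0.84 + 0.50 + 0.22) = 92.2. Only differences between models are therefore relied on below.

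**3. Adding p = 1 term.** The variance becomes 4V(1−R²)/n × (n−3)/(n−4). Break-even at a single look is R² = 1/(n−3): 3.0%, 1.4%, 1.0% and 0.7% at 36, 72, 108 and 144. Over the whole design it is about 1.6% for power and 1.4% for expected N.

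| Model | Power | Expected N |
|---|---|---|
| Stratum only | 0.904 | 83.5 |
| Added term, R² 0 | 0.900 | 83.9 |
| R² 2% | 0.905 | 83.3 |
| R² 5% | 0.912 | 82.5 |
| R² 10% | 0.925 | 80.9 |
| R² 20% | 0.947 | 77.3 |

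**4. Which rows are reachable?** Morphine equivalents overlap with the stratum and are probably near zero in most non-users. If they inform only among chronic users, and residual variance is similar in both strata, the extra R² is the user share times the R² within users.

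| Assumed user share | Within-user R² for break-even (1.55%) | Power at within-user R² 5% | Power at within-user R² 20% |
|---|---|---|---|
| 10% | 16% | 0.901 (extra R² 0.5%) | 0.905 (2%) |
| 20% | 8% | 0.902 (1%) | 0.910 (4%) |
| 30% | 5% | 0.904 (1.5%) | 0.915 (6%) |

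An extra R² of 10% would need perfect prediction among users at a 10% share (0.10/0.10), 50% at 20% and 33% at 30%. An extra R² of 20% is impossible at a 10% share and needs perfect prediction at 20%. In a separate simulation with 10 to 25% users and assumed slopes of 0.2 to 0.6 pain points per log unit, the standard error ratio ran from about 1.00 to 0.976. The best case is about 5% of variance, since 0.976² = 0.953.

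**5. Against the uncertainty of the inputs.** The same recursion gives power 0.914 at SD 2.45 and 0.893 at SD 2.55. It gives 0.920 at correlation 0.55 and 0.887 at 0.65. The plan calls both inputs approximate, and its internal pilot reassesses them at the second look.

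**The case for a change.** The strongest case is that the trade is lopsided. The variable is already collected. A useless term costs about 0.4 power points and 0.4 patients in expected N, while an extra R² of 5 to 10% would bring 0.9 to 2.1 points. The term can be fixed in advance only now; once unblinded data have been seen, adding it would be post hoc.

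The arithmetic stands, and a sponsor that made this choice before any unblinded look would be doing nothing wrong. Three things weaken the case.

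- **Evidence of gain.** The Background statements concern opioid requirement and sensitivity, not pain score in recovery. Wide variation among chronic users does not show that recorded dose explains it, and the same section says many of the factors are unknown or poorly documented. Fentanyl is titrated in both arms, and rescue analgesia and PCA follow in recovery. These may offset baseline differences before or while pain is scored.
- **Cost.** More than one sentence is needed. A skewed variable calls for a chosen transformation and a missing-value rule. With 5% of values missing and those patients dropped, power at R² 5% is 0.899, below the planned model. Dropping them would also depart from the analysis set of "all randomized patients receiving any of the study intervention".
- **Knock-on to the internal pilot.** The plan says "we will use the observed within-patient correlation from the linear mixed effects model and the standard deviation at each time point". Pairing a raw SD with a correlation from the adjusted model would overstate the variance by about 3% at R² 5% and 7% at R² 10%, so that calculation would need changing too.

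One caveat favours the objection: if non-users also differ usefully in last-month opioid use, the ceilings in step 4 loosen. The document gives no information on this.

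**Conclusion.** The concern does not hold. The stratum-only model matches the stratified randomisation, is consistent with the plan's other adjusted models, and reaches its stated power (0.904 by recursion, target 90%). An added term for morphine equivalents would move power to between 0.901 and 0.915 under the assumed user shares of 10 to 30% and within-user R² of 5 to 20%, and to 0.900 if it explains nothing. The sign of the change is not settled, because the document gives no figure for what the variable explains beyond the stratum.

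This rests on the plan's SD and correlation, on reading V as the variance left after the stratum, on complete covariate data, and on the printed boundaries. It does not depend on agreement with the printed crossing probabilities, because only differences between models are used. Leaving the covariate out of a model first tested at 36 patients, where break-even is 3.0%, is a reasonable design choice. Adding it would be another.

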  - c. Muscle relaxants
  - d. Reversal agents
2. Events:
  - a. Induction
  - b. Intubation
  - c. Foley catheter placement
  - d. Incision
  - e. Insufflation
  - f. Trocar insertion
  - g. Discontinuation of sevoflurane
  - h. Extubation

In recovery, patients will be asked to rate their pain at rest on a 0-10 verbal response scale. Measurements will be taken at 10-minute intervals from awakening until 60 minutes has elapsed. Somnolent patients will be given a score of "S" for queries to which they are unable to respond. Patients will simultaneously be asked to rate nausea on a 0-10 scale. Sedation will be evaluated with the Ramsay score, also at 10-minute intervals.

Episodes of vomiting during the initial 60 minutes of recovery will be recorded. The time and dose of any administered postoperative analgesics or anti-emetics will be recorded.

The trial will end after 60 minutes of recovery and all subsequent management will be per clinical routine.

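### The secondary relative-risk model leaves out the time effect that the primary model includes, and the sensitivity and Ramsay models do not say whether they contain it

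*Combined protocol and SAP*

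**What the plan says.** Data Analysis describes three repeated-measures models for pain and one for sedation.

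- **Primary (linear mixed model):** "fixed effects for intervention, time (as categorical) and the stratification variable of pre-operative chronic opioid use". A separate sentence follows: "We will also assess the treatment-by-time interaction".
- **Sensitivity (proportional odds, random patient effect):** described as "while estimating the proportional odds ratio for patients having a better outcome on NOL than standard care, again adjusting for the stratification variable". Time is not mentioned.
- **Secondary (log-link model for a score below 5):** "with treatment group and the stratification variable as fixed effects". The same treatment-by-time sentence follows, and the result is reported as a relative risk.
- **Exploratory Outcome 2 (Ramsay):** a proportional odds model fitted "in the same manner as described for the sensitivity analysis for the primary outcome", with the rule that "NOL will be deemed noninferior if the upper confidence limit for the odds ratio is less than 1.2".

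The Measurements section gives somnolent patients a score of S "for queries to which they are unable to respond". Data Analysis has no rule for handling S. The secondary hypothesis treats a relative increase of 10% or more in good scores as clinically meaningful.

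**The concern.** Only the secondary model has an explicit fixed-effect list that leaves time out. The treatment-by-time sentence does not repair it: the primary paragraph carries the same sentence in addition to a time main effect, so it describes a further step and not the model that yields the reported relative risk.

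A trend over the hour is plausible. Human Subjects Protection puts typical initial pain at 7/10, and the Protocol section has rescue boluses and PCA starting on arrival. Unequal early loss is also plausible, because Exploratory hypothesis 3 expects faster emergence with NOL guidance. If one arm supplies fewer early readings, a model without time attributes part of the time trend to treatment.

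The odds-ratio models raise a different issue. Leaving out a strong predictor moves a conditional odds ratio toward 1 even when no data are missing. For Ramsay that odds ratio is compared with a fixed margin.

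**Working it through.** **The plan's own figure.** The documents give no power, odds ratio or relative risk for these models. Their nearest figure is the fixed-design total of 116, from SD 2.5, correlation 0.60, difference 1.25, 90% power and alpha 0.05 (taken as two-sided). The SD of a patient's mean over m readings is 2.5 × √((1 + (m−1) × 0.6)/m).

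- m = 7: SD 2.027, total 112 (normal) or 114 (t).
- m = 6: SD 2.041, total 114 (normal) or 116 (t).

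The inputs therefore reproduce the plan's figure to within two patients by the t calculation. They are used below.

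**Secondary relative risk.** Without time, and ignoring correlation weights, the model compares the average proportion of good scores over the readings available in each arm: Σ(1 − loss) × p / Σ(1 − loss). Assume good scores rise linearly from 30% to 70% over 7 readings (sum 3.5) with no true effect. Assume loss at the first two readings of 50% and 30% in routine care, and 20% and 10% in NOL.

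- Routine: (3.5 − 0.5 × 0.300 − 0.3 × 0.367) / (7 − 0.8) = 3.240/6.2 = 0.5226.
- NOL: (3.5 − 0.2 × 0.300 − 0.1 × 0.367) / (7 − 0.3) = 3.403/6.7 = 0.5080.
- Ratio: 0.972. With the losses reversed it is 1.029.

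| Assumed rise in good scores | True RR | More loss in routine | More loss in NOL |
|---|---|---|---|
| none (50%) | 1.10 | 1.100 | 1.100 |
| 40% to 60% | 1.10 | 1.084 | 1.116 |
| 30% to 70% | 1.10 | 1.069 | 1.132 |
| 20% to 80% | 1.10 | 1.055 | 1.147 |

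With no loss or equal loss, the value is 1.100 in every row. As a check, a log-link GEE (a marginal stand-in for the planned mixed model; 20,000 simulated patients, 30% to 70% trend) gave 1.068 and 1.134 without time, and 1.097 and 1.098 with time.

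A second set of scenarios takes P(score < 5) = Φ((4.5 − mean)/2.5), with mean pain falling from 7 to 4, 7 to 5.5, 6 to 4 or 7 to 3, and a true relative risk of 1.

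| Loss at readings 1 and 2 | RR without time |
|---|---|
| 40% routine, 20% NOL at both | 0.965 to 0.980 |
| Reading 1 lost in both arms; 40% vs 20% at reading 2 | 0.982 to 0.990 |
| Routine 100% and 50%; NOL 50% and 10% | 0.913 to 0.950 |

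**Odds ratio with complete data.** A random-intercept cumulative logit model was fitted to 6,000 simulated patients (SD 2.5, correlation 0.60, 1.25-point effect), with and without categorical time. Compare within a row; differences between rows include simulation error.

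| Assumed fall in pain | OR with time | OR without time | Ratio of log ORs |
|---|---|---|---|
| 0 | 4.68 | 4.68 | 1.00 |
| 1 point | 3.87 | 3.72 | 0.97 |
| 2 points | 4.32 | 3.69 | 0.89 |
| 3 points | 4.44 | 3.30 | 0.80 |
| 4 points | 4.25 | 2.79 | 0.71 |

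**Ramsay margin.** Let f be the ratio of log odds ratios, borrowed from the pain simulation, and assume the standard error shrinks by the same f. A true odds ratio of 1.2 is then estimated as 1.2^f: 1.193 at f = 0.97 and 1.138 at f = 0.71. For N = 144, SE ≈ √(4 × (2.221² + (π²/3)/7)/144) = 0.387. The one-sided error is Φ(log 1.2 × (1 − f)/(SE × f) − 1.96), which gives 0.0259 at f = 0.97 and 0.0385 at f = 0.71, against 0.025. If the limit is taken at a nominal one-sided 0.05, the corresponding values are 0.0515 and 0.0731.

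**The case against.** **Silence is not exclusion.** The sensitivity paragraph says only "again adjusting for the stratification variable", immediately after a primary model that contains time, and Ramsay refers back to it. A reader might infer that all three models exclude time. The documents support that only for the secondary model; the other two are unspecified. This objection stands.

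**Shorthand.** Assessing an interaction normally implies its main effects, so time probably enters the secondary interaction model. That is fair, but the reported relative risk comes from the model whose listed effects omit time.

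**No documented trend.** The documents give an initial pain level but no course for pain or Ramsay, and no Ramsay data were simulated. This also stands: with no trend, nothing changes.

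**Size.** A reader might infer that the bias could consume most of the 10% threshold. That needs the extreme case in which routine care loses every first reading and NOL only half, and nothing in the documents points to such a split. If the first reading is lost in both arms and 40% versus 20% at the second, the bias is 1 to 2%.

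**Estimand, not validity.** With complete data, the smaller odds ratio is a different conditional quantity. Its standard error shrinks with it, so the test of no effect changes little. The sensitivity analysis therefore keeps most of its value as a check on direction and significance. Power for Ramsay is in any case only about 7% at a true odds ratio of 1 under the assumed SE, so the margin issue is minor.

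**Conclusion.** The point holds in a limited form, as a free improvement. The secondary model as listed omits time; the sensitivity and Ramsay models should state whether they include it.

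- **Relative risk:** with a trend and moderately unequal early loss, the bias is roughly 1 to 4%. It is about a third of the 10% threshold in the 30% to 70% scenario and somewhat more under the steepest trend assumed. Its sign depends on which arm loses more readings. It is zero with complete or equal loss.
- **Odds ratios:** with complete data, log odds ratios are about 3 to 29% smaller for an assumed 1 to 4 point fall. With unequal loss they can also shift either way.
- **Ramsay:** one-sided error of about 0.026 to 0.039 instead of 0.025, given an assumed SE of 0.39 and shrinkage borrowed from pain.

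The text of the secondary model is certain; the sizes depend on assumed trends and losses. The primary analysis, the 116 and 144 patients and the stopping boundaries are unaffected.

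**What to change.** In Data Analysis:

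1. Add time (categorical, 7 levels) to the fixed effects of the secondary model.
2. State the same term explicitly in the proportional odds sensitivity model and in Exploratory Outcome 2.
3. Say that treatment-by-time is tested only in a model that contains the time main effect.

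This is one phrase in three places plus a clarifying sentence, with no extra patients or data. It removes the bias from unequal loss that depends only on time, and puts the odds ratios on the same time-conditional footing as the primary model. It does not correct S scores that are informative within a time point, because patients too sedated to answer may differ from those who answer. The handling of S needs its own rule.
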